
5. STUDY POPULATION

5.1 Inclusion Criteria

- 1. Male or females >18 years old \geq 6months after kidney transplantation;
- 2. In patients with T2D or PTDM, HbA1c <12.0%;
- 3. eGFR \geq 30 ml/min/1.73m² (as per the CKD-EPI equation⁷⁰);
- 4. BMI $\leq 45 \text{kg/m}^2$;
- 5. Blood pressure $\leq 160/90$ and $\geq 90/60$ at screening.

5.2 Exclusion Criteria

1. Diagnosis of type 1 diabetes;

March 18, 2022

- 2. Presence of severe peripheral vascular disease (i.e. prior amputation, gangrene, nonhealing ulcer or ischemic rest pain);
- 3. Presence of acute coronary syndrome, stroke or transient ischemic attack in the 3 months prior to screening;
- 4. Prior episode of graft pyelonephritis in the 1 month prior to screening;
- 5. Episode of acute graft rejection in the 3 months prior to screening;
- 6. Initiation of a new immunosuppressive agent or discontinuation of an immunosuppressive agent in the 1 month prior to screening;
- 7. Untreated urinary or genital tract infection;
- 8. Severe hypoglycemia within 3 months of screening, or hypoglycemia unawareness;
- 9. Pre-menopausal women who are nursing, pregnant, or of child-bearing potential and not practicing an acceptable method of birth control;
- 10. Participation in another trial with an investigational drug within 30 days of informed consent;
- 11. Alcohol or drug abuse within 3 months prior to informed consent that would interfere with trial participation;
- 12. Any ongoing clinical condition that would jeopardize subject safety or study compliance based on investigator judgement.
- 13. Patients currently using antipsychotic medications.
- 14. Use of SGLT2 inhibitors within 1 month of starting the study.

5.3 Sample Size

The sample size is based on the primary endpoint of blood pressure. Currently, there is only one publication from our group with information available on the effect of SGLT2i on blood pressure reduction in KTR with diabetes. In this observational study of 10 KTR and simultaneous pancreas-kidney transplant recipients treated with canagliflozin, we reported a SBP decrease of $6.5 \pm 10 \text{ mmHg}^{63}$. Given the small sample size in our observational study, we believe the standard deviation would be smaller in a larger cohort. Blood pressure reduction with SGLT2 inhibition appear to be similar between patients with and without diabetes in non-transplant studies. We, therefore, estimated the sample size based on a SBP change of 6.5 mmHg with a standard deviation of 8 mmHg. Under the hypothesis that SGLT2i decreases SBP by $6.5 \pm 8 \text{ mmHg}$ compared to placebo with a two-sided alpha of 0.05 and 80% power, we calculate a sample size of n=48, with 24 randomized to dapagliflozin and 24 randomized to placebo. Assuming a 10% attrition rate, the final sample size required is 52 participants. This sample size is similar to those successfully used in previous studies⁷¹, and sufficient to measure secondary renal endpoints related to renal hemodynamic function⁷¹, natriuresis and arterial stiffness⁷²⁻⁷⁴. Based on previous studies, we anticipate an even sex distribution in each group.

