95. [name] DZ, Miller JA, Scholey JW, Bradley TJ, Slorach C, Curtis JR, Dekker MG, Nasrallah R, Hebert RL and Sochett EB. The effect of cyclooxygenase-2 inhibition on renal hemodynamic function in humans with type 1 diabetes. *Diabetes*. 2008;57:688-95.

96. [name] DZ, Sochett EB, Lai V, Dekker MG, Slorach C, Scholey JW and Bradley TJ. Renal hyperfiltration and arterial stiffness in humans with uncomplicated type 1 diabetes. *Diabetes care*. 2010;33:2068-70.

15. Tables and Figures.

Figure 1: Effects of SGLT2 inhibition on the nephron.

Figure reproduced from: van Bommel EJ. Et al. SGLT2 Inhibition in the Diabetic Kidney-From Mechanisms to Clinical Outcome. *Clin J Am Soc Nephrol*. 2017;12:700-710.

[figure not shown]

Figure 2: Potential cardio- and renoprotective mechanisms of SGLT2 inhibition.

Figure reproduced from: Heerspink HJ. et al. Sodium Glucose Cotransporter 2 Inhibitors in the Treatment of Diabetes Mellitus: Cardiovascular and Kidney Effects, Potential Mechanisms, and Clinical Applications. *Circulation*. 2016;134:752-72.

[figure not shown]

Figure 3: Study design

Continuation of existing therapy including immunosuppression, anti-hypertensives, glycemic medications

			1		
SCREENING Visit 1	BASELINE Visit 2 Visit 3	WEEK 1 ACUTE Visit 4	DOSING Visit 5 Visit 6 Visit 7	WEEK 12 CHRONIC Visit 8 Visit 9	Follow UP Visit 10

Observational	Observational studies							
Author, Year	Participants	Design	Treatment	Results				
Rajasekeran et al. Diabetes Care 2017 ¹ Mahling et al.	N=10 KTR & SPKTR with PTDM or T2D N=10 KTR with	Observational cohort study, 80.5 person- months follow- up Observational	canagliflozin	Weight, kg: -2.14 (SD 2.8) Systolic blood pressure, mmHg: -6.5 (SD 10.8) Diastolic blood pressure, mmHg: -4.8 (SD 12) Serum creatinine, mmol/L: 9.7 (SD 14.6); eGFR, mL/min/1.73 ² : -4.3 (SD 12.2) No urinary/mycotic infections, AKI or acute rejection Weight, kg: -1.9 (-1.9 to 0.1)				
Kidney Blood Press Res 2019 ²	PTDM or T2D	study, 6.3 person-years		Systolic blood pressure, mmHg: -2.5 (-36.3 to 0.8) Diastolic blood pressure, mmHg: -0.5 (-9.5 to 7.5) 2 episodes of UTI, 1 episode of AKI				

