Alkindi et al. Transplant Proc 2020 ³	N=8 KTR with PTDM or T2D	Retrospective chart review	empagliflozin (6 patients), dapagliflozin (2 patients)	BMI , kg/m ² , 32.7 \pm 7.2 to 27.4 \pm 4.2 after 12 months (p<0.05) Systolic blood pressure , mmHg: 135 \pm 9.6 to 126.4 \pm 11.5 after 12 months (p>0.05) Diastolic blood pressure , mmHg: 80.6 \pm 10 to 74.5 \pm 7.3 after 12 months (p>0.05) eGFR , no significant change 1 episode of UTI, no AKI, ketoacidosis, acute rejection				
Schwaiger et al. AJT 2018 ⁴	N=14 KTR with PTDM, 6 months post-transplant, eGFR \geq 30ml/min/1.73m ² , stable on insulin therapy	Open-label, single-arm, non- inferiority study Single-centre study	Treatment with empagliflozin 10mg after discontinuation of insulin therapy, 4 weeks	Change in baseline to 4 week OGTT - fasting and 2-hour glucose levels increased to $144 \pm 45 \text{ mg/dL}$ (P = .005) and $273 \pm 116 \text{ mg/dL}$ (P = .06), respectively Avg body weight: -1.6kg; Bioimpedance volume status: fluid overload decreased from 2.7 ± 2.1 (baseline) to 1.8 $\pm 1.8L$ (P = .006) 5 episodes of urinary tract infection				
Randomized C		Γ	Γ					
Author, Year	Participants	Design	Treatment	Results				

Table 1: Summary	v of studies of SGLT2i in kidney	y trans	plant reci	pients.
Observational st	-diag			

Halden et al.	N=49 KTR with	Double-blind	1:1	Secondary Outcomes
Diabetes	PTDM, 1 year post	RCT	empagliflozin	Change in median HbA1c (%): -0.2 (-0.6 to -0.1) with
Care ⁵	transplant, eGFR	Single centre	10mg vs.	empagliflozin vs +0.1 (-0.1 to 0.4); p=0.025
	\geq 30m/min/1.73m ²	study	placebo, 24	Body Weight : -2.5 kg (-4.0 to -0.05) with empagliflozin
			weeks	vs +1.0 kg (0.0 to 2.0); p=0.014
				24hr blood pressure – no difference in blood pressure
				between groups
				Safety Outcomes – no significant between group
				differences

KTR: Kidney transplant recipients; SPKTR: Simultaneous pancreas-kidney transplant recipients; T2D: Type 2 diabetes; PTDM: Post-transplant diabetes mellitus; eGFR: Estimated glomerular filtration rate; SD: Standard deviation. OGTT: Oral Glucose Tolerance Test

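### Section 5.3 takes its 6.5 mmHg difference from placebo from an uncontrolled pre-post fall in 10 patients, leaves out the other Table 1 blood pressure data, and quotes power at that one effect only.

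*Protocol*

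**What the plan says.** Protocol section 5.3 "estimated the sample size based on a SBP change of 6.5 mmHg with a standard deviation of 8 mmHg". It then treats that change as the decrease relative to placebo and states that "with a two-sided alpha of 0.05 and 80% power, we calculate a sample size of n=48", split equally at 24 per arm. It continues: "Assuming a 10% attrition rate, the final sample size required is 52 participants".

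The 6.5 mmHg has one source: "In this observational study of 10 KTR and simultaneous pancreas-kidney transplant recipients treated with canagliflozin". Section 5.3 gives its SD as 10; section 2.5 and Table 1 give 10.8. The choice of source is introduced by "Currently, there is only one publication from our group with information available on the effect of SGLT2i on blood pressure reduction in KTR", and the sentence ends by restricting itself to recipients with diabetes.

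Table 1 lists blood pressure results from three other studies in kidney transplant recipients with diabetes, none of which section 5.3 mentions:

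- An observational study of 10 recipients: "Systolic blood pressure, mmHg: -2.5 (-36.3 to 0.8" (bracket closes there).
- A chart review of 8 recipients: mean systolic pressure 135 mmHg, falling to 126.4 mmHg at 12 months, p>0.05.
- A double-blind randomized trial of empagliflozin against placebo in 49 recipients with post-transplant diabetes (PTDM), over 24 weeks: "24hr blood pressure – no difference in blood pressure" between groups. No estimate or interval is shown.

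**The concern.** A before-after fall in treated patients is not a difference from placebo. It also contains whatever would have happened without the drug: regression to the mean, time trends and changes in other treatment. A planning value taken from it may be too large, and the source has no control arm from which to tell. The source also used a different SGLT2 inhibitor in patients with eGFR above 60 (section 2.5), whereas this trial admits eGFR from 30.

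The one placebo-controlled blood pressure result that the protocol lists goes undiscussed where the planning effect is justified. The primary objective is superiority on systolic pressure, and power is quoted at a single effect. A non-significant result could then be read against a nominal 80% although the trial had much less power for a smaller effect.

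**Working it through.** **Inputs from section 5.3.** Difference 6.5 mmHg, SD 8 mmHg, two-sided alpha 0.05, power 80%, 1:1 allocation, 24 per arm, 10% attrition, final N 52.

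**1. The plan's own figure.** n per arm = 2 × SD² × (1.960 + 0.842)² / difference² = 2 × 64 × 7.85 / 42.25 = 23.8, so 24 per arm and 48 in total. Power at 24 per arm is 80.4% by the normal approximation and 78.7% by the noncentral t. The stated N is reproduced.

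**2. Precision of the source.** With n = 10 and the Table 1 SD of 10.8, SE = 10.8/√10 = 3.42. The 95% interval for the mean fall is 6.5 ± 2.262 × 3.42, or −1.2 to 14.2 mmHg (p = 0.09). With the SD of 10 given in section 5.3, SE = 3.16 and the interval is −0.7 to 13.7. Both include zero, before any allowance for the missing control group.

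**3. Power at other effects.** Table 1 gives no placebo-adjusted estimate, so the effects below 6.5 mmHg are assumptions chosen to show a range. The unadjusted column is a two-sample t-test at 24 per arm with SD 8. The SAP's primary model (its analysis section 1.1) has no treatment main effect, so the arms share a baseline mean and the analysis gains from baseline adjustment. That gain is approximated by multiplying the change-score SD by √((1+ρ)/2), where ρ is the correlation between baseline and follow-up. The documents do not give ρ; 0.5 to 0.76 is assumed, which makes the effective SD 6.93 (ρ = 0.5) to 7.50 (ρ = 0.76).

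| True placebo-adjusted effect | Unadjusted t-test | Baseline-adjusted, ρ 0.76 to 0.5 |
|---|---|---|
| 6.5 mmHg (planned) | 79% | 84–89% |
| 5 mmHg (assumed) | 56% | 62–69% |
| 4 mmHg (assumed) | 40% | 44–50% |
| 3 mmHg (assumed) | 25% | 27–31% |

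**4. The other Table 1 studies.** The two uncontrolled falls are 2.5 mmHg and 135 − 126.4 = 8.6 mmHg. They lie on either side of 6.5, and neither is a difference from placebo. The randomized trial supplies no number to plan from.

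**5. Attrition.** 48 / (1 − 0.10) = 53.3, which rounds up to 54. Conversely 52 × 0.90 = 46.8, so 46 to 47 completers are expected at 10% attrition. An N of 52 leaves 48 completers only if attrition is at most 1 − 48/52 = 7.7%. At 6.5 mmHg and SD 8, unadjusted power is 76.9% with 46 completers and 77.8% with 47, against 78.7% with 48.

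**The case against.** The strongest reply has four parts.

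- *The source sentence is literally true.* It speaks of publications from the investigators' own group, in recipients with diabetes. A reader might infer that Table 1 contradicts it. Read as written, it does not: the other studies come from other groups, and section 2.5 refers the reader to Table 1. This stands. The fault is that section 5.3 uses the evidence selectively.
- *The randomized trial is not a match.* A reader might infer that it shows no blood pressure effect in this trial's population. It enrolled only PTDM recipients, one year after transplant, and compared 24-hour blood pressure on empagliflozin over 24 weeks. This trial enrols recipients with or without diabetes from six months after transplant, and measures seated automated office pressure on dapagliflozin at 12 weeks. A report of no difference in 49 patients, without an interval, does not show a zero effect and does not rule out 6.5 mmHg. This also stands. It is a reason to discuss the result, not to pass over it.
- *The planned analysis is stronger than the t-test.* If 6.5 mmHg is right and SD 8 holds, baseline adjustment puts power above the stated 80%. This stands, subject to the assumed correlation, but it does not restore 80% at 5 mmHg or below.
- *Attrition is already covered.* Section 9.6 lets new patients be admitted after withdrawals to reach the required number, and the loss of power is about one to two percentage points. This stands, so the attrition point is only a correction of a figure.

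**Conclusion.** The concern holds in a limited form. The arithmetic in section 5.3 is sound. What is unsupported is the use of an uncontrolled and imprecise fall (95% interval about −1.2 to 14.2 mmHg) as the placebo-adjusted effect, with no discussion of the other evidence in the protocol's own table. The 80% is conditional on 6.5 mmHg and SD 8. Over assumed effects of 3 to 5 mmHg, power is 25–56% unadjusted and 27–69% with baseline adjustment at an assumed correlation of 0.5 to 0.76.

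A reader might go further and conclude that the trial is probably underpowered. The documents do not support that: they contain no placebo-adjusted estimate, and one of the uncontrolled falls, 8.6 mmHg, exceeds the planning value. The supportable statement is that power is unknown over a plausible range and should be shown as such.

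All these figures keep the stated SD of 8, which was itself lowered from the source value. At 6.5 mmHg without baseline adjustment, t-test power would be 60% with SD 10 and 53% with SD 10.8. The attrition shortfall is real but has little effect.

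**What to change.** Keep N at 52 and revise section 5.3:

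1. State that 6.5 mmHg is a pre-post change without a control group, from 10 patients on canagliflozin, and give its interval.
2. Replace the sentence about the group's own publication with a short account of all the blood pressure evidence in Table 1. Include the randomized trial and how its drug, population, blood pressure measure and duration differ from this trial's.
3. Replace the single 80% with power at, for example, 3, 4, 5 and 6.5 mmHg. Label the effects, and any baseline correlation used, as assumptions.
4. Correct the attrition sentence: 52 allows 7.7% attrition, or leaves 46 to 47 completers at 10% before any replacement under section 9.6.

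The cost is wording only. Recruitment, endpoint and analysis are unchanged, and the stated power becomes less favourable at effects below 6.5 mmHg.

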2.5 SGLT2i in kidney transplant recipients: Current state of knowledge

Currently, there are few published experiences on the use of SGLT2i in transplant recipients⁶³ (**Table 1**). To our knowledge, the use of SGLT2i has also been described in a few other immunosuppressed populations including heart transplant recipients. We studied 10 KTR and simultaneous pancreas-kidney transplant recipients and showed that the use of use of the SGLT2 inhibitor canagliflozin was associated with improvements in glycemic control (hemoglobin A1c (HbA1c) -0.84 \pm 1.2 %), weight (-2.14 \pm 2.8kg) and blood pressure (systolic -6.5 \pm 10.8 mmHg and diastolic -4.8 \pm 12 mmHg), which were similar in magnitude to effects reported in non-transplant cohorts. Furthermore, we did not observe any episodes of ketoacidosis, AKI, acute rejection or urinary/mycotic infections during treatment. One patient experienced hypoglycemia, and one patient developed cellulitis. Finally, there were no clinically significant changes in CNI

levels. However, this was a small cohort of patients with excellent kidney function (eGFR >60ml/min/1.73m²) where canagliflozin was initiated several years after transplantation, with a limited follow-up of 80.5 person-months. In order to better understand the efficacy, safety and potential mechanisms of SGLT2i in this unique population with variable degrees of renal impairment, further comparative studies are needed in larger cohorts of KTR.

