9. METHODS

9.1 Study parameters/endpoints

9.1.1 Main study parameter/endpoint

The primary outcome of this study is blood pressure (SBP) reduction. Blood pressure will be measured using a calibrated automated office oscillometric device with a proper sized cuff, as per the Hypertension Canada Guidelines⁷⁹. Patients will be seated comfortably for 5 minutes. After this period of rest, blood pressure will be obtained on 3 occasions with at least 1 minute between measurements. The first measurement will be discarded, and an average of the subsequent two measurements will be recorded. Similar methodology for blood pressure measurement has been used in previous clinical trials in KTR²⁶. Furthermore, patients with CKD have a higher prevalence of peripheral vascular disease and increased arterial stiffness as compared to the general population. As a result, the first SBP measurement may be less accurate as compared to subsequent measurements in patients with CKD⁸⁰. Blood pressure will be measured at the following time points during the study: Day 0 (baseline), day 7 (1 week), day 42 (6 weeks), day 84 (12 weeks) and day 91 (13 weeks).

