11. STATISTICAL ANALYSIS

The analytical plan mirrors that operationalized in previous work^{92, 93}. Data will be analyzed using Stata/SE 15. The primary outcome is the difference in blood pressure reduction in dapagliflozin vs. placebo treated participants at 12 weeks. Secondary outcomes will consist of within and between group changes metabolic, vascular, renal and transplant outcomes. Frequency of adverse events, non-adherence and drug discontinuation will be tabulated (no comparisons will be made). Within group comparisons will be analyzed using repeated measures ANOVA (baseline value will be included in these ANOVA models). As in previous work, between group comparisons will also be made using a 2-way ANOVA with treatment as the dependent variable^{71, 92, 94-96}. This clinical trial is not sufficiently powered to detect sex- or gender-based differences. However, data analyses will be stratified by sex and gender to detect any similarities or differences. These will be exploratory analyses and hypothesis generating, which may be informative in the design of future studies. Other exploratory analyses will include stratification by GFR (measured iohexol GFR of <45 ml/min/1.73m² vs. >45 ml/min/1.73m²), as well as diabetes type (T2D and PTDM). An intention-to-treat (ITT) approach will be used. Adherence will be measured (see '**Randomization**' in the proposal), and non-adherent patients will also be included in the ITT analysis.

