# 1. Analysis for the primary objective:

- 1.1. To assess dapagliflozin-related acute and chronic changes in the primary outcome of seated systolic blood pressure compared to placebo, linear mixed-effects models will be used. Two separate models will be fit. For acute change, the vector of outcomes will include the baseline and 1-week values (i.e. Visit 3 and Visit 4 values). For chronic changes, the vector of outcomes will include the baseline and 12-week values (i.e. Visit 3 and Visit 9 values). The covariates will include the visit and treatment-by-visit interaction; due to randomization, a covariate for the main effect of treatment will not be included. The treatment-by-time coefficient, its 95% confidence interval, and its p-value will be used to assess the effect of treatment.
- 1.2. We will repeat this analysis with:
  - a. Seated diastolic blood pressure as an outcome
  - b. Seated mean arterial pressure as an outcome

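### Protocol 5.3 supports its planning SD of 8 mmHg only with an invalid reason and misquotes the pilot SD, so the stated 80% power rests on an unsupported assumption

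*Protocol*

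**What the plan says.** Protocol 5.3 bases the sample size on systolic blood pressure. It cites the group's observational study of 10 recipients treated with canagliflozin and gives the fall as 6.5 with an SD of 10 mmHg. It then argues: "Given the small sample size in our observational study, we believe the standard deviation would be smaller in a larger cohort". On that footing the authors "estimated the sample size based on a SBP change of 6.5 mmHg with a standard deviation of 8 mmHg". With two-sided alpha 0.05 and 80% power this gives 48 participants, 24 per arm, raised to 52 for 10% attrition.

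Two other places report the same 10 patients with a different SD. Section 2.5 has "systolic -6.5 \pm 10.8 mmHg", and Table 1 has "Systolic blood pressure, mmHg: -6.5 (SD 10.8".

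The SAP contains no power calculation, SD or correlation. Its primary model (SAP analysis section 1.1) is a mixed model with visit and treatment-by-visit terms, and "due to randomization, a covariate for the main effect of treatment will not be included". The baseline mean is therefore common to both arms, which gains precision over a comparison of raw changes. Protocol section 11 still describes a different analysis: "between group comparisons will also be made using a 2-way ANOVA with treatment as the dependent variable".

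**The concern.** The step from the pilot SD to 8 mmHg carries the whole calculation, and the reason given for it is a statistical error. Enlarging a study reduces the standard error of the mean and makes the SD estimate more stable. It does not lower the SD in the population. A pilot of 10 has an imprecise SD, not an inflated one; on average a sample SD at n=10 is slightly too low (about 0.973 of the true value under normality).

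Nothing else in 5.3 supports 8. The remark on patients with and without diabetes concerns the size of the fall in blood pressure, and the comparison with previous studies concerns the number of participants. The pilot figure that 5.3 starts from is also the more favourable of the two in the protocol.

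The 80% is the only power stated for the primary endpoint. A null result at 12 weeks would be read against it, and a reader of 5.3 cannot see how far it depends on the SD.

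**Working it through.** **Inputs.** Difference 6.5 mmHg, SD 8, two-sided alpha 0.05, 80% power, 24 per arm (Protocol 5.3). Pilot SD 10 (5.3) or 10.8 (2.5, Table 1), n=10. Model: SAP 1.1, random intercept, REML. The baseline to 12-week correlation ρ is **not in the documents**; 0.3 to 0.7 is assumed. All SDs are taken as SDs of within-patient change, the same in both arms.

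**1. The plan's own figure.** n per arm = 2 × (1.960 + 0.842)² × SD² / 6.5².
- SD 8: 23.8, so 24 per arm and 48 in total. The plan's figure reproduces.
- SD 10: 37.2. SD 10.8: 43.3.

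At SD 8 with 24 per arm, power is 80.4% by the normal formula and 78.7% by noncentral t. That small gap comes from t versus normal only.

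**2. How much the pilot says about the SD.** The 95% CI is √(9 × 10.8² / χ²₉), which runs from 7.4 to 19.7 under normality. SD 8 is inside, near the lower end. If the true SD were 8, a sample of 10 would show 10.8 or more about 6% of the time.

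**3. Unadjusted t-test, 24 per arm.** The noncentrality is 6.5 / (SD × √(2/24)) on 46 df.
- SD 8: 6.5/2.309 = 2.815
- SD 10: 6.5/2.887 = 2.252
- SD 10.8: 6.5/3.118 = 2.085

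**4. SAP 1.1 model, 24 per arm.** With equal variances at both visits, the effective SD is SD × √((1+ρ)/2), on 45 df. Example: SD 10.8 and ρ = 0.5 give 10.8 × √0.75 = 9.35.

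| SD of change | t-test | SAP model, ρ = 0.7 | SAP model, ρ = 0.3 |
|---|---|---|---|
| 8 | 78.7% | 84.8% | 92.7% |
| 10 | 59.7% | 66.6% | 78.0% |
| 10.8 | 53.2% | 60.0% | 71.6% |

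At SD 10.8 and ρ = 0.5 the SAP model gives 65.4%. Widening ρ to 0.8-0.2 gives 57.6-75.0%. Simulating the random-intercept REML model at SD 10.8 (400 runs per value, t on 45 df) gave 71%, 68% and 60% at ρ = 0.3, 0.5 and 0.7, in line with the formula.

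**5. If all 52 are evaluable (26 per arm).** Unadjusted power is 81.9%, 63.3% and 56.7% at SD 8, 10 and 10.8. Under the SAP model at SD 10.8 it is 63.6-75.1% for ρ = 0.7-0.3.

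**6. Detectable difference.** At SD 10.8 with 24 per arm, 80% power needs 8.9 mmHg unadjusted, or 8.2 to 7.2 mmHg under the SAP model for ρ = 0.7-0.3.

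**7. Attrition.** 52 × 0.9 = 46.8, not 48.

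**The case against.** The strongest reply is that a planning SD is a judgement and that 8 may well be right. The arithmetic at SD 8 is sound, and neither 10 nor 10.8 enters it. SD 8 is compatible with the pilot. The pilot is also a weak benchmark: 10 kidney or pancreas-kidney recipients on another SGLT2 inhibitor, observed without a control group for 80.5 person-months in total. Its SD may not transfer, in either direction.

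The trial has features that could lower the SD. Section 9.1.1 standardises the readings ("The first measurement will be discarded, and an average of the subsequent two measurements will be recorded"), and 9.3 controls diet before the main study days. The SAP model adds reserve: at SD 8 it gives about 85-93% over the assumed correlations. The SD at which it still reaches 80% is about 7.87/√((1+ρ)/2), or 8.5 to 9.8 for ρ = 0.7-0.3. The planning SD does not enter the analysis, so neither the estimate nor the type I error is affected.

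All of this stands, and it limits the point. A reader might infer that the trial is underpowered or that 48 is miscalculated. The documents support neither reading. The reply does not supply the missing reason, since 5.3 invokes neither the measurement method nor the diet. It does not make the quoted sentence valid or reconcile 10 with 10.8. Nor does the SAP model restore 80% at SD 10.8 for any correlation from 0.2 to 0.8.

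On attrition, 9.6 allows new patients to be admitted after withdrawals, so 52 is not an error. Section 5.3 simply does not say that it relies on this.

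**Conclusion.** The point holds as one about justification and disclosure. The only reason offered for SD 8 is invalid, and the pilot SD is misquoted in the section that relies on it. SD 8 is unsupported, not disproved, and 48 is correct if it holds.

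The size is the gap between the stated 80% and the power at the pilot's own SD of 10.8: 53% by unadjusted t-test and about 60-72% under the SAP 1.1 model. At the SD of 10 that 5.3 itself quotes, the figures are 60% and about 67-78%.

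The SAP-model ranges rest on an assumed correlation of 0.7-0.3, equal variances at the two visits, and the same SD of change in both arms. They cover the 12-week comparison only, not the 1-week one that the SAP also names as primary.

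**What to change.** Change the wording of 5.3 only:

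- Delete the sentence saying that the SD would shrink in a larger cohort.
- Correct the pilot SD to 10.8 and give its 95% CI (7.4 to 19.7). Add that the pilot was uncontrolled and used another SGLT2 inhibitor, so its SD may not transfer in either direction.
- Give a valid reason for SD 8, for example the averaged readings in 9.1.1 or the diet control in 9.3 if these are relied on. Otherwise label it an assumption.
- State power for 6.5 mmHg at 12 weeks with 24 per arm at SD 8, 10 and 10.8. By unadjusted t-test this is 79%, 60% and 53%. Under the SAP 1.1 model it is about 85-93%, 67-78% and 60-72%, with the correlation of 0.7-0.3 marked as an assumption. Cite the SAP as the source of that model, because Protocol section 11 still describes an ANOVA.
- Minor: say that 52 with 10% attrition leaves about 47, and that reaching 48 relies on replacement under 9.6.

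The target of 52 stays, and enrolment, procedures and analysis do not change. The cost is a less favourable stated power at the pilot SD.

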9.6 Replacement of individual subjects after withdrawal

Patients that meet inclusion criteria will be invited for participation in the study. When patient agrees to participate in the study, informed consent is signed. When patient decides to withdraw after start of the treatment period, new patients can be admitted to the study to reach the required sample size.

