#### 5. Pre-specified post-hoc analyses:

- 5.1. The same models described in the analysis of primary objective 1.1 will be performed for the outcome.
- 5.2. The same models described in the analysis of exploratory objective 3.2 will be completed for each of the different outcomes.

Analysis population: The intention to treat population will be used for all analyses.

*Hypothesis testing:* For hypothesis testing, a 5% significance level will be used (two-sided). No interim analyses will be performed. For secondary objectives, nominal p-values will be reported.

*General model assumptions and model diagnostic procedures:* For the linear mixed-effects models with visit and treatment-by-visit interaction as covariates, a participant-level random intercept will be included. Restricted-maximum-likelihood will be used for estimation and the missing-at-random framework will be assumed. Plots of marginal and conditional residuals will be used for model diagnostics and assessment. Similar diagnostic procedures will be used for the linear regression models.

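### Section 5.3 states 52 for 48 evaluable participants at 10% attrition; those inputs give 54, and 52 covers 7.7% (a minor arithmetic error)

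*Protocol*

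**What the plan says.** Protocol section 5.3 sets out the calculation in one paragraph. The assumed effect is an "SBP change of 6.5 mmHg with a standard deviation of 8 mmHg", "compared to placebo with a two-sided alpha of 0.05 and 80% power". From this, "we calculate a sample size of n=48, with 24 randomized to dapagliflozin and 24 randomized to placebo". The paragraph then closes the calculation with "Assuming a 10% attrition rate, the final sample size required is 52 participants". The figure of 52 is repeated in the secondary objectives (section 3.2) and the study design (section 4).

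Two other places bear on the point. Protocol section 9.6 says that when someone withdraws after treatment has started, "new patients can be admitted to the study to reach the required sample size". The SAP's closing paragraphs say that "The intention to treat population will be used for all analyses" and that "Restricted-maximum-likelihood will be used for estimation and the missing-at-random framework will be assumed". The primary model (SAP, analysis for the primary objective, 1.1) places the baseline and the follow-up reading together in the outcome vector and omits a main effect of treatment.

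**The concern.** Two adjacent statements in section 5.3 do not fit together. If 48 evaluable participants are needed and 10% are lost, 52 is too few, because 10% of 52 is more than the 4 participants separating 52 from 48. The usual cause is multiplying by 1.10 where the calculation should divide by 0.90. Here 48 × 1.10 = 52.8, which becomes 52 if the fraction is dropped. The protocol does not show the step, so this route is a guess.

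At stake is whether the trial's headline sample size delivers what the paragraph says it does. There is no reserve in the 48: it is the smallest equal-arm size that reaches 80% on the formula that reproduces it. Any shortfall in completers therefore takes the calculation below its stated target.

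**Working it through.** **Inputs (all Protocol section 5.3).** Difference 6.5 mmHg; SD 8 mmHg; two-sided alpha 0.05 (z = 1.960); power 80% (z = 0.842); equal arms; attrition 10%; final size 52.

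**Step 1: reproduce the 48.** Two-sample normal formula, per arm:

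n = 2 × SD² × (1.960 + 0.842)² / difference² = 2 × 64 × 7.849 / 42.25 = 23.78, rounded up to 24.

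The total is 48, which matches the protocol exactly. A one-sided test would give 19 per arm and a t-test calculation 25, so the plan appears to use the two-sided normal formula.

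**Step 2: the attrition allowance.**

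- Required number randomised: 48 / (1 − 0.10) = 53.3, which is 54 in equal arms.
- Expected completers from 52: 52 × 0.90 = 46.8.
- Attrition that 52 does cover: (52 − 48) / 52 = 4/52 = 7.7%.
- From the unrounded requirement, 2 × 23.78 = 47.56: dividing by 0.90 gives 52.84, which rounds up to 53. Multiplying by 1.10 gives 52.3, which reaches 52 only by rounding to the nearest integer.

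**Step 3: power at the reduced number.** Power = Φ(6.5 / SE − 1.960), with SE = 8 × √(1/n₁ + 1/n₂).

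| Completers | SE | Power, normal | Power, t test |
|---|---|---|---|
| 24 + 24 = 48 | 2.309 | 80.4% | 78.7% |
| 24 + 23 = 47 | 2.334 | 79.5% | 77.8% |
| 23 + 23 = 46 | 2.359 | 78.7% | 76.9% |

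On the protocol's own formula the shortfall is 0.5 to 1.3 points below 80%. The t-test column is lower throughout, but it is already at 78.7% with the full 48. That part of the gap comes from the choice of formula, not from attrition.

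**Step 4: the chance of keeping 48.** Suppose each participant independently has a 10% chance of being lost (an assumption made here). At least 48 then complete with probability 40% when 52 are randomised (at most 4 losses) and 71% when 54 are (at most 6 losses).

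**Step 5: the planned model.** Suppose that SD 8 is the SD of the change in SBP, and that SBP has the same variance at baseline and week 12, with correlation ρ. The documents state neither the equal variance nor ρ. A model that constrains the arms to share a baseline mean, as the SAP's does, then multiplies the variance of the treatment effect by (1 + ρ)/2 relative to a comparison of change scores. With 23 completers per arm, SE = 2.359 × √((1 + ρ)/2):

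| ρ (assumed) | SE | Power, normal | Power, t test |
|---|---|---|---|
| 0.5 | 2.043 | 88.9% | 87.5% |
| 0.7 | 2.175 | 84.8% | 83.2% |
| 0.9 | 2.299 | 80.7% | 78.9% |

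On the normal formula, 46 completers still give 80% if ρ is below about 0.93. That follows from setting 6.5/SE = 2.802, so SE = 2.320 and (1 + ρ)/2 = (2.320/2.359)² = 0.967.

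**The case against.** The strongest reply is that the gap is rounding-sized and has no consequence. Against the unrounded requirement of 52.84, the figure of 52 is less than one participant short, and power at the expected 46.8 completers is 79.4%. The 10% is itself a round planning guess. This stands as a statement of size. It does not make the sentence correct: sample sizes are rounded up to protect power, and the paragraph itself takes 48 as the number it needs.

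A second reply is that section 9.6 lets the sponsor replace people who withdraw on treatment. If replacement continues until 48 have completed, the shortfall disappears, so the figure of 46 to 47 completers is conditional. But topping up a full 52 takes enrolment above the stated number, and section 9.6 does not say whether its required size means 48 completers or 52 randomised. Replacement can rescue the power; it does not rescue the arithmetic in section 5.3.

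A third reply concerns the analysis. A reader might infer from the shortfall that the trial misses its 80% power. The documents do not support that reading. The 79% belongs to an unadjusted two-sample comparison, whereas the SAP specifies a mixed model that uses the baseline reading and may exceed 80% with 46 completers. Participants who leave after baseline also stay in that model, though they add little on the 12-week contrast. The offset cannot be claimed as fact either, because it depends on reading SD 8 as the SD of change and on a correlation that the documents do not give.

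**Conclusion.** The point holds as a minor error: the sentence in section 5.3 is wrong as written. The stated inputs give 54 in equal arms; 52 allows for 7.7% attrition and leaves about 46 to 47 completers at 10%. On the formula that reproduces the 48, power is then about 79% instead of 80%. This rests on the protocol's difference of 6.5 mmHg and SD of 8, on drop-outs not being replaced, and on an analysis that gains nothing from baseline.

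The error does not threaten the trial. The choice of SD is a separate and larger question for power: section 5.3 itself reports an SD of 10 from the earlier series, at which 24 per arm would give about 61% on the same formula. Moving from 52 to 54 would not settle that question.

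**What to change.** Keep 52 and replace the attrition sentence in Protocol section 5.3 with wording such as:

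> 52 participants allow for about 8% attrition (4 of 52). At 10% attrition about 46 to 47 would complete, giving about 79% power by the two-sample normal approximation used here.

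In section 9.6, state whether replacements are in addition to the 52, and whether the size to be reached means participants randomised or participants completing.

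If the sponsor prefers to keep the 10% claim, the alternative is to change 52 to 54 here and in sections 3.2 and 4, at the price of two more participants. The recommended wording costs one sentence in section 5.3 and a clarification in section 9.6. It adds no participants and leaves the design and analysis unchanged. The only loss is a slightly less favourable power statement.
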